1. INTRODUCTION

Bullying victimization can harm victims' mental health. Numerous studies have shown that, when an adolescent is a victim of cyberbullying, the risk of developing numerous mental health problems increases. Some of the most well-known problems are depression and social anxiety^{1,2} but recent studies indicate that eating disorders are also common—because cyberbullying often attacks the victim's body image¹—as are self-harming behaviors, especially of a non-suicidal nature³. In addition, these sequelae could be more prominent among girls¹.

In the last decade, cyberbullying has been added to presential victimization. Like traditional bullying, online forms of bullying affect victims' health mental health and well-being negatively². Although the forms of offline and online psychological abuse coexist in relationships, there are a few factors that suggest that these are different problems. For example, in online abuse, the abusive messages and images may be forwarded by third parties, which implies some revictimization⁴. In addition, once an image, video, or information is disseminated on the Internet by the perpetrator, it can remain in cyberspace indefinitely, which means that the aggression can be extended and reach many people, making the humiliation especially harmful for the victim⁵. Finally, online victimization and bullying are mainly indirect, rather than face-to-face. The aggressor does not see the victim's reaction immediately, which can facilitate insensitivity and lack of empathy towards the victim and make it easier for those who would not dare to harass a classmate face-to-face to do so in online settings.

Tackling the problem of cyberbullying victims' worsening mental health involves at least (1) reducing bullying itself, as this would reduce the prevalence of victimization, and (2) building resilience in the victims so that their mental health does not worsen. In recent years, a number of preventive interventions have been developed aimed at reducing cyberbullying⁶ but not so much focused on building resilience in the victims. Numerous experts indicate that the solution lies less in mitigating risks and dangers, and more in developing factors of protection and resilience to address the social and emotional problems linked to victimization⁷. In fact, previous interventions are valuable,

but they present some areas of improvement that pose challenges to scientific psychology. One such area of improvement is not specific to these interventions, but to all preventive interventions aimed at adolescents in general. Thus, according to important and rigorous meta-analytical studies, the effectiveness of these interventions is extremely limited. For example, in a review of 22 studies that examined the effects of interventions on peer bullying, only 11 studies (50%) showed significant effects in its reduction⁸. Interventions aimed at building resilience to potential victimization are even more limited, and yet, in recent years, the importance of developing programs aimed not only at reducing the risk of being a victim but also developing social and emotional protection against such victimization has been indicated^{7,9}.

Why do interventions for adolescents and young people fail?

Based on the results of various meta-analyses, the degree of development of a child or adolescent can act as an important variable that will moderate the impact of intervention programs^{10,11}. However, there is some debate about how this moderation takes place. Some authors conclude that anti-bullying programs and programs to reduce other risky behaviors are more effective among adolescents than among children¹⁰. In contrast, other reviews and meta-analyses have concluded that the effects of interventions are minor in adolescence. For example, through hierarchical meta-analysis¹¹, they concluded that the effectiveness of traditional anti-bullying programs is limited as of adolescence, just at a time when these programs are extremely necessary.

Many universal preventive interventions are based on decision-making theories. They come from the premise that, if adolescents are provided with aspects such as risk information, as well as coping skills training, emotion regulation, and education in appropriate values, behavioral change will be facilitated. In this way, numerous interventions have been carried out aimed at preventing problems such as depression and bullying behaviors⁶. However, some features of adolescence can cause these approaches to fail. Compared to children, adolescents are more sensitive to being treated with respect and to the acknowledgment of their status and autonomy¹². Therefore, if adolescents perceive that adults are trying to manipulate them or introduce behavior patterns that threaten their autonomy, they will often resist. In contrast, younger children can more easily

accept adult authority and curricular activities voluntarily¹³.

Wise interventions: a new approach

Very recently, scientific social psychology has shown increased interest in a new approach to interventions, which have been labeled "*wise interventions*". This approach involves a set of rigorous techniques, based on theory and research, that address specific psychological processes to help people improve in various life environments (for a review, see Walton & Wilson¹⁴). Wise interventions emphasize the subjective creation of meanings and how people interpret themselves and social situations. In this way, they can effectively change behavior recursively over time. These types of interventions have been applied to problems that can have a significant cost at personal, social, and economic levels. Many of these interventions have outstanding results because they tend to be very short and produce lasting changes in people's behavior. Indeed, in recent years, a proliferation of wise interventions has addressed countless social and personal problems. Thus, some wise interventions have been shown to improve academic performance, facilitate the social integration of young people from ethnic minorities, and reduce depression and aggressive behavior (Walton & Wilson¹⁴).

These types of interventions are of great interest in adolescence, as they can be designed so they are perceived as respectful towards the students' autonomy and status, so that the students will realize that they make their own decisions¹². In fact, the results obtained with these types of interventions in adolescent behaviors are hugely promising. For example, Yeager and collaborators designed a universal brief intervention aimed at changing implicit beliefs about adolescent personality. This intervention, which teaches participants that "people can change" was effective in reducing symptoms of anxiety and depression and aggressive behavior in young people^{15,16}. Recently, our team has adapted this intervention to Spanish adolescents and has carried out several studies to evaluate its effectiveness in depression and peer and partner bullying, obtaining important indicators of its effectiveness through randomized clinical trials. A relevant aspect of the findings is that the adolescents' degree of evolutionary development moderates the effects of the interventions. Thus, in those adolescents with a lower degree of pubertal development (biologically evaluated), or from lower academic courses, the intervention was more

effective^{17,18}. This intervention included materials related to offline contexts, so in this project, we propose that the intervention can be modified and adapted to online scenarios to be more effective to prevent cyberbullying and its impact on victims' mental health.

2. OBJECTIVES AND HYPOTHESES

The main objective of this project is to extend the previous findings to the mental health effects of online victimization in adolescents. We shall design and evaluate the effectiveness of an wise intervention aimed at (1) reducing online bullying, as this would reduce the prevalence of victimization; and (2) building resilience in victims so that the negative impact of victimization on their mental health will be reduced. The working hypotheses are that (1) the frequency of aggressive online behaviors among adolescents receiving the intervention will be reduced compared to the control group, and (2) the intervention will buffer the predictive relationship between victimization and mental health problems (anxiety, depression, eating disorders, and self-injurious behavior).

The secondary objective will be to evaluate the moderating role of gender and the degree of development in the effects of the intervention. As the results of meta-analytical studies for some psychological problems indicate that preventive interventions are more effective in the most vulnerable groups¹⁹, gender is expected to moderate the effectiveness of the intervention, such that it will be more effective for behaviors that are most prominent for each gender. In this way, for example, the effect on eating disorders or depression is expected to be greater in girls than in boys. As for the degree of evolutionary development, the results of previous studies are inconsistent, with some pointing to greater effectiveness of preventive interventions in adolescents than in children¹⁰ and others pointing in the opposite direction¹². Contributing new empirical evidence to help clarify the inconclusive findings of previous studies is of great importance for the adequate timing of the implementation of preventive interventions. Finally, potential change mediators such as attitudes towards cyberbullying and the intention to use stress management strategies will be explored.

3. METHODOLOGY

Design and Procedure

An experimental study will be carried out with two parallel groups. Participants will complete an online evaluation protocol through Qualtrics, including different questionnaires at three measurement times: (1) pretest (one week before the intervention), (2) 3-month follow-up, and (3) 6-month follow-up.

The study will be carried out with the approval of the Ethics Committee of the University of Deusto. Informed consent from parents and adolescents will be required. Participants should not indicate their first and last names on the completed protocols, which will be paired over time through a code known only to each participant.

Participants

Recruitment will take place through schools. Participants will be students of Secondary Compulsory Education (SCE) and high school. The final sample will be approximately 600 adolescents (300 in each group). The proportion of participants will be balanced according to gender and educational level, as the role of both variables as potential moderators of the effectiveness of the intervention will be examined.

Interventions

Two intervention models both of similar duration (approximately 1 hour) and structure will be used, and the wise intervention will be compared to an educational control intervention.

1. Wise Intervention: Continuing with the line of work of the previous projects, the intervention will be based on four general types of change strategies: (1) scientific knowledge, (2) generation of new meanings, (3) commitment through action, and (4) active reflection. This will include activities such as reading scientific information about social behavior and its role in people's well-being and mental health, the meaning of online victimization experiences and ways to react to them, experiences of other young people of their age, and self-persuasion exercises that involve an active commitment to change.

2. Educational control intervention. The control intervention will involve scientific information and education about internet risks such as sexting and grooming. It will have a parallel format to the wise intervention and a similar duration.

Measures

The objective variables of this research will be measured through pre-validated self-report questionnaires with evidence of appropriate psychometric properties:

The Spanish-adapted and validated version²⁰ of the **Functional Assessment of Self-Mutilation** (FASM²¹) scale will be used to evaluate self-reported self-harm by adolescents. The FASM scale measures Non-Suicidal Self-Harm (NSSH) through several questions divided into three parts. The 6 most representative items of its first part will be used. It presents a list of forms of self-harming behaviors without suicidal intent about which participants are requested to indicate whether or not they occurred in the last year, as well as their approximate frequency. These NSSH behaviors can be classified as moderate/severe or minor, depending on their severity. The FASM scale has shown good psychometric properties, both internal consistency and convergent validity, with measures of suicidal ideation and hopelessness and post-traumatic and/or depressive symptoms. The Spanish version has also shown suitable psychometric properties in adolescent samples²⁰.

The Spanish and brief version²² of the scale of the **Center for Epidemiologic Studies-Depression** [CES-D]²³) will be used to analyze depressive symptoms. The brief CES-D consists of 10 items associated with depressive symptoms, to be rated on a four-point Likert frequency scale ranging from 0 (*practically never*) to 3 (*almost all the time*). It has a sensitivity of 77.8% and a specificity of 74.1%. The CES-D has been widely used in adolescents, showing appropriate psychometric properties of reliability for the Spanish-adapted version (Cronbach α = .83²³ including the short version (Cronbach α = .86)²².

The symptomatology of social anxiety will be evaluated with the short form²⁴ of the Spanish version of the **Social Anxiety Scale for Adolescents** (SAS-A²⁵). The short form of the SAS-A contains 12 items that measure three factors of social anxiety: Fear of Negative Assessment, Anxiety in New Situations, and General Social Avoidance. The items are rated on a five-point scale, ranging from 1 (*not at all*) to 5 (*all the time*). The Spanish version showed

adequate psychometric properties²⁵, for example, excellent alpha coefficients (Cronbach α = .92).

A short version of the **Eating Attitudes Test**²⁶ (EAT-8²⁷) will be used to evaluate the symptomatology associated with eating disorders. The EAT-8 is a self-reporting screening questionnaire consisting of 8 items. A six-point response scale ranging from 1 (*never*) to 6 (*always*) will be used for this study. The EAT-8 has shown satisfactory psychometric properties in the general population²⁷.

The reduced version of the **Cyberbullying Questionnaire** (CBQ) will be used to measure the degree of victimization and perpetration of cyberbullying²⁸. It consists of two subscales of 9 items (each) that evaluate the frequency of (a) victimization and (b) perpetration. Participants respond on a five-point frequency scale, ranging from 0 (*never*) to 4 (*5 or more times*). The CBQ has adequate psychometric properties of convergent and construct validity and internal reliability.

The eight-item **Implicit Theories of Personality**²⁹ questionnaire will be used to evaluate the degree to which theories about malleability (incremental theory) or stability (entity theory) of personality are adopted. The items were adapted to bullying situations in schools (e.g., "bullies and victims are types of people who can't really change"). Response options are rated on a seven-point scale, ranging from 1 (*completely disagree*) to 6 (*completely agree*), with higher scores indicating stronger adoption of the entity theory (i.e., the belief that people do not change). The psychometric properties of internal consistency in samples of Spanish adolescents are good (Cronbach α = .83).

Ad hoc measures will be included to assess attitudes towards cyberbullying and behavioral intentions. To evaluate the intention to use different strategies when the adolescent is exposed to diverse stressors, participants will complete six items on a four-point response scale ranging from 0 (*never or almost never*) to 3 (*always or almost always*). Some examples of items are: "Talking to someone else so they can listen to me and help me," "Doing sports or some exercise".

Ethical considerations

This study aims to develop and implement interventions that will be beneficial for the participating adolescents and other people in the future, by helping to increase their psychological well-being. Through randomization, the principle of justice will be respected, allowing all participants to have similar opportunities to receive the intervention. Gender will be considered and a similar number of male and female participants will be included in each condition.

The risks are minimal and limited to answering psychological tests on stressors, psychological symptoms, and cognitive styles. Previous experience with the same questionnaires indicates that the risk is minimal. Adolescents can also decide to end their participation at any moment. Researchers collecting data will be trained to attend to any difficulty that could emerge while participants are responding to the questionnaires. The researchers will give an alternative task (e.g., educational readings) to those participants who decide to end their participation.

Informed consent forms will be sent to parents or legal guardians and adolescents will also receive information.

After completing measures, adolescents will be provided with information on services for adolescents (e.g., phone number of attention to adolescents). From an ethical perspective, the most important care aspect is the protection of information. We will follow the Directive 95/46/EC of the European Parliament, *Organic Law 15/99 of 13 December of Personal Data Protection*, and of the Council of 24 October 1995 on the protection of individuals concerning the processing of personal data and the free movement of such data. No identification data, such as names or surnames, will be used; instead, we will use a numeric code to match measures across times and sources. Thus, each adolescent, and only they, will know their code. We will also follow the procedure for data protection that the University of Deusto has registered in the National Data Protection Agency. The project has been approved by the Ethics in Research Committee of the University of Deusto.

Statistical analysis Plan

We shall use various statistical analysis strategies, including Hierarchical Linear Modeling with HLM 7.03, using the FIML estimation method. Level 1 will include repeated measures in the dependent variables (cyberbullying, depression, social anxiety, eating disorders, and self-harming behaviors). Level 2 will include the experimental condition, using dummy variables, together with gender and educational level (through dummy variables), as well as the interaction terms between experimental conditions and those variables. The third level will include the average level of cyberbullying in the classroom in which the participant is located to control its influence. The moderating effect of the intervention on the longitudinal relationship between victimization and mental health will also be evaluated by structural equation modeling with the LISREL 9.2 and MPLUS-7 programs.

References

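### Self-harm has only a last-year recall window; if it is used at every wave, 75% of the recalled period at 3 months and 50% at 6 months predates the session, which dilutes any effect on this outcome

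*Combined protocol and SAP*

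**What the plan says.** The Measures part of section 3 describes six FASM items on which "participants are requested to indicate whether or not they occurred in the last year, as well as their approximate frequency". It does not say whether the yes/no answer or the frequency is analysed, and gives no separate wording for follow-up.

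The Design and Procedure part of section 3 plans an online protocol "including different questionnaires at three measurement times: (1) pretest (one week before the intervention), (2) 3-month follow-up, and (3) 6-month follow-up". Each intervention lasts about one hour, so the session can be treated as a point in time.

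In the Statistical analysis Plan, "Level 1 will include repeated measures in the dependent variables (cyberbullying, depression, social anxiety, eating disorders, and self-harming behaviors". Condition enters one level higher: "Level 2 will include the experimental condition, using dummy variables, together with gender and educational level (through dummy variables". Nothing there says how time is coded or whether pretest is an outcome or a covariate.

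Section 2 includes self-harm in hypothesis 2: "the intervention will buffer the predictive relationship between victimization and mental health problems (anxiety, depression, eating disorders, and self-injurious behavior".

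**The concern.** A follow-up outcome should mostly reflect what happened after the intervention. A twelve-month window asked three months after a one-hour session mostly does not. An adolescent who self-harmed shortly before the session and then stopped could truthfully answer yes at both follow-ups, so a real change would be partly hidden.

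Two things are at stake. A null self-harm result would say less about the intervention than it appears to. And hypothesis 2 is a predictive claim about buffering, which can begin only after the session, while the later self-harm scores would largely report the same months as the pretest score.

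**Working it through.** **Inputs from the documents.** Recall window 12 months (Measures). Pretest one week, about 0.25 month, before the session; follow-ups at t = 3 and t = 6 months (Design and Procedure). About 300 per group (Participants). The plan gives no overlap or power figure for self-harm, so there is none to reproduce.

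**Share of the window before the session** = (12 − t)/12.
- 3 months: (12 − 3)/12 = 75%.
- 6 months: (12 − 6)/12 = 50%.
- If follow-up is counted from the pretest, the shares are 76.9% and 51.9%. The plan does not state the origin, but it hardly matters here.

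**Overlap of windows** = 12 minus the gap between waves.
- Pretest and 3 months: 12 − 3.25 = 8.75 months.
- 3 and 6 months: 12 − 3 = 9 months.
- Pretest and 6 months: 12 − 6.25 = 5.75 months.

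**Dilution.** With a constant event rate, a 40% cut in the rate after the session appears as 40% × 3/12 = 10% in last-year frequency at 3 months and 40% × 6/12 = 20% at 6 months.

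For a yes/no outcome, assume 30% annual prevalence. The monthly rate is λ = −ln(0.7)/12 = 0.0297.
- Last year, month 3, treated: 1 − exp(−λ(9 + 0.6 × 3)) = 27.5%, against 30.0% in controls.
- Last year, month 6, treated: 1 − exp(−λ(6 + 0.6 × 6)) = 24.8%, against 30.0%.
- Last 3 months, either follow-up: 1 − exp(−0.6 × 3λ) = 5.2%, against 1 − exp(−3λ) = 8.5%.

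**Power illustration by simulation.** This is not the planned HLM or SEM. Only the 300 per arm comes from the documents. Assumed: 30% annual prevalence, 40% rate reduction, Poisson events, no clustering or dropout, two-sided 5% test. Frailty means that individual rates vary (gamma, shape 0.5). The month-3, month-6 and two-follow-up tests are linear models adjusted for pretest with robust standard errors. The slope test uses each person's least-squares slope from pretest, unadjusted. Monte Carlo error is about 0.01, and repeat runs differ by 0.01 to 0.03.

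| Test | Scoring | Last year | Last 3 months |
|---|---|---|---|
| Month 3 | yes/no | 0.17 | 0.38 |
| Month 6 | yes/no | 0.37 | 0.37 |
| Both follow-ups averaged | yes/no | 0.32 | 0.64 |
| Both follow-ups averaged | yes/no, frailty | 0.24 | 0.63 |
| Both follow-ups averaged | count | 0.38 | 0.64 |
| Month 6 | count | 0.45 | 0.38 |
| Slope from pretest | yes/no | 0.27 | 0.19 |
| Slope from pretest | yes/no, frailty | 0.24 | 0.26 |
| Slope from pretest | count, frailty | 0.44 | 0.25 |

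With a 20% reduction, the two-follow-up test has power of about 0.12 vs 0.19. With no effect, rejection rates stay near 0.05.

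Hypothesis 2 is a moderation, so the two-follow-up test was also run as a victimization-by-condition interaction. With 30% victims, a rate ratio of 2.5 and complete buffering (a strong assumption), power is 0.28 vs 0.66.

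**The case against.** The strongest reply is that the plan describes what the FASM contains, not the wording at each wave. That stands: use of the last-year window at follow-up is implied by the repeated-measures plan but not stated. It does not clear the plan. If the wording is kept, the outcome is diluted. If a shorter window is intended only at follow-up, it is missing from the plan, and a last-year pretest would not be comparable with it.

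Second, the gain depends on the analysis. That also stands. The plan does not specify a pretest-adjusted contrast over both follow-ups, and a condition-by-time slope is a natural reading of its HLM. A reader might infer that shortening the window is an improvement by itself; the slope rows and the month-6 count row show otherwise.

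Third, a reader might infer that old events favour the intervention. The documents do not support this. Assignment is randomized ("Through randomization, the principle of justice will be respected, allowing all participants to have similar opportunities to receive the intervention"), so earlier self-harm is balanced in expectation; what is lost is effect size and precision.

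Fourth, one might read the overlaps as the share of cases in which self-harm preceded victimization. The cyberbullying questionnaire has no stated recall window ("It consists of two subscales of 9 items (each) that evaluate the frequency of (a) victimization and (b) perpetration"), so no such share can be derived.

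Finally, a weakly informative null is only partly due to the window: power is at best about 0.65 even after the change, and low either way for a 20% reduction.

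**Conclusion.** The point holds as dilution of one outcome, conditional on the last-year wording being used at follow-up. The 75% and 50% shares follow directly from the plan's own window and schedule. The power figures are illustrative and rest on an assumed prevalence, effect and event process. They support a limited statement: a short window roughly doubles power for a pretest-adjusted test over both follow-ups in the base case, and can lower power under a linear slope from pretest.

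For hypothesis 2, post-session buffering would be mixed with self-harm from before the session. Hypothesis 1 and the anxiety, depression and eating outcomes are not touched by this wording. It should be fixed, but it does not undermine the trial as a whole.

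**What to change.** Make two changes together.

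1. In Measures, state the self-harm recall period and scoring for each wave. Use a window of the same length throughout that does not reach back before the session at follow-up, for example the last 3 months at pretest, 3 months and 6 months. Keep the last-year question at pretest for description only. State whether follow-up is counted from the session: if it is counted from pretest, a 3-month window at the first follow-up still takes in the week before the session.
2. In the Statistical analysis Plan, test condition over the two follow-ups with pretest self-harm as a covariate (or with pretest means held equal between arms), not as a linear slope from pretest. Use the same short-window score in the SEM.

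If the slope analysis is kept, the case for rewording on power largely disappears, and the plan should say which trade-off it accepts. Stating the recall window of the cyberbullying questionnaire would also settle the time order for hypothesis 2.

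Cost: rewording six online items, a short pretest addition and a few lines of analysis text; no extra participants. Downsides: lower prevalence per wave (8.5% instead of 30% in the illustration), less comparability with last-year results, and a changed recall period in an instrument from a set that, according to the plan, "will be measured through pre-validated self-report questionnaires with evidence of appropriate psychometric properties". The week between pretest and session would fall outside the 3-month windows if follow-up is counted from the session.

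### The planned HLM puts condition, dummy-coded gender and educational level, and their products in one model and names no overall contrast, so its condition term is a reference-category effect, not the overall effect in hypothesis 1

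*Combined protocol and SAP*

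**What the plan says.** All references are to the combined protocol and SAP.

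- **Hypothesis 1** (section 2) is an overall group comparison: "the frequency of aggressive online behaviors among adolescents receiving the intervention will be reduced compared to the control group". It is not limited to one gender or school stage.
- **Moderation** is ranked below it in the same section: "The secondary objective will be to evaluate the moderating role of gender and the degree of development in the effects of the intervention". An interaction is predicted: "gender is expected to moderate the effectiveness of the intervention".
- **The model** (section 3, Statistical analysis Plan) has repeated measures of the outcomes at Level 1. For the next level it says "Level 2 will include the experimental condition, using dummy variables", and continues "together with gender and educational level (through dummy variables), as well as the interaction terms between experimental conditions and those variables". The third level carries the classroom average of cyberbullying.
- **The sample** (section 3, Participants): "The final sample will be approximately 600 adolescents (300 in each group)". On the moderators: "The proportion of participants will be balanced according to gender and educational level". Two school stages are named, compulsory secondary education and high school. The number of educational-level dummies is not given.

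The plan does not mention a main-effects-only model, staged entry of terms, centring, effect coding, reference categories or an averaged contrast. It does not say which coefficient answers hypothesis 1.

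**The concern.** In a model with 0/1 dummies and products, the coefficient of condition is the effect when every dummy that multiplies it is zero, that is, for one gender at one educational level. This applies in whichever Level 2 equation carries the intervention effect, the intercept or the change over time. It equals the overall effect only if the interactions are zero or happen to cancel at the reference categories.

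The plan does not expect that. It predicts moderation by gender, and the Introduction reports that in earlier trials, among adolescents "from lower academic courses, the intervention was more" effective. An analyst who fits the model as listed and reads the condition row would report a quantity that changes with the choice of reference category and has a wider confidence interval than the overall effect. A null result on hypothesis 1 could then come from the coding alone.

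**Working it through.** The plan gives no power, alpha, effect size or intraclass correlation, so there is no stated figure to reproduce. The check is about what the coefficient means and how precisely it is estimated.

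**Inputs from the documents.** N = 600, 300 per group; balance over gender and educational level; dummies for both moderators, and their products with condition.

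**Assumptions.** Individual allocation, one post-baseline outcome with SD 1, no clustering or dropout, two-sided alpha 0.05, equal-sized levels, two-way products only. The number of levels k is 2 for the two named stages; larger k is an assumption about coding by school year.

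**1. What the coefficient estimates.** Take k = 2 and assumed effects of -0.10 SD in the reference cell, a further -0.20 for the other gender and +0.10 for the other level.
- Average effect: -0.10 + (0.5 × -0.20) + (0.5 × 0.10) = -0.15.
- Least squares on the dummy-coded model gives -0.10. Changing only the reference categories moves this to 0.00, -0.30 or -0.20.
- With the indicators mean-centred before the products are formed, the coefficient is -0.15 whatever the reference.

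**2. Precision.** In the balanced layout the variance of the estimated effect at a given gender and level is

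Var = (4/N) × [1 + D(gender) + D(level)],

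where each D is the squared standardised distance of that category from the sample mean.
- Overall effect: both distances are zero, so Var = 4/600 and SE = 0.0816.
- Reference gender, half the sample: D = 0.5² / 0.25 = 1.
- Reference level, one of k equal levels: D = k - 1.
- Variance ratio: 1 + 1 + (k - 1) = k + 1.

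**3. Power.** An effect with 80% power for the overall contrast has a standardised distance of 1.960 + 0.842 = 2.80, that is d = 2.80 × 0.0816 = 0.229. For the condition term this distance is divided by √(k + 1):

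| k | Variance ratio | SE | SE ratio | Power |
|---|---|---|---|---|
| 2 | 3 | 0.141 | 1.73 | 37% |
| 3 | 4 | 0.163 | 2.00 | 29% |
| 4 | 5 | 0.183 | 2.24 | 24% |
| 6 | 7 | 0.216 | 2.65 | 19% (18.5%) |

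Inverting the design matrices numerically gives the same ratios. With mean-centred indicators the ratio is 1.0 for every k. The contrast averaged over the sample, taken from the dummy-coded fit, also has ratio 1.0.

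**4. A recoding that does not work.** Coding each level indicator ±0.5 gives the average effect only when k = 2. Take six levels with an assumed effect running linearly from -0.30 to 0 (mean -0.15). The condition term is then +0.15 with the first level as reference and -0.45 with the last, and its variance ratio is 21. Mean-centring gives -0.15 in both cases.

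**The case against.** The strongest reply is that the plan never says the condition coefficient tests hypothesis 1. It lists which variables sit at each level, presents HLM as one of several strategies, and would be compatible with main effects first and products second. Centring is unmentioned, not excluded. This stands. A reader might infer that the trial has committed itself to the wrong estimand for hypothesis 1, and the text does not support that. What remains is that the only model described does not yield the overall contrast directly, and no other route to it is prespecified.

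Other points that stand:

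- The overall effect can be recovered from the same fit at full precision, so power is lost only if the wrong row is read.
- A reader might infer that the coefficient uses only the reference cell. With two-way products every participant contributes. Estimation from that cell alone would give variance ratios of 4 (k = 2) and 12 (k = 6), not 3 and 7, and arises only if a three-way product is added.
- Six levels appear nowhere in the documents; only the two-stage case follows from the named stages.
- The gender examples in section 2 are eating disorders and depression, with no direction given for online aggression, and the same section calls earlier results on development inconsistent. The plan therefore supports expecting heterogeneity, but not its size or direction for hypothesis 1.
- Hypothesis 2 is about buffering the link between victimization and mental health, which the plan also assigns to structural equation modelling. A reader might extend the point to hypothesis 2; the documents state no overall condition effect on the mental-health outcomes as a hypothesis.

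**Conclusion.** The point holds as an unspecified contrast. In the Level 2 model as written, with ordinary 0/1 dummies, the condition term is the model-based effect at an unstated reference gender and educational level. It is not the overall effect of hypothesis 1, and nothing else in the plan supplies that effect.

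The meaning of the coefficient is algebra and needs only 0/1 coding with products. The variance ratio of k + 1 also needs balance, individual allocation and no clustering: 3 for the two named stages, and larger, for example 7, if six school years were coded. The power figures (80% to 37%, or to about 19%) further assume an effect of 0.229 SD and two-sided alpha of 0.05. They come from a single-outcome calculation rather than the full repeated-measures model, so they are illustrative.

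Because the remedy needs no new data and the fitted model already contains the answer, this is a free improvement to the plan and not a flaw in the design.

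**What to change.** Add to the Statistical analysis Plan: *Hypothesis 1 is tested from a model with condition, gender and educational level as main effects; moderation is tested in a second model that adds the products.*

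If a single model is preferred, either of these serves the same purpose:
- mean-centre the gender and educational-level indicators before forming the products; or
- report the condition contrast averaged over the enrolled sample from the fitted model.

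State which Level 2 equation (intercept or change over time) carries the intervention effect, how many educational levels are coded, and the reference categories. Do not use ±0.5 coding for the level indicators when there are more than two levels. Use the same coding for any overall condition effect reported for the other HLM outcomes.

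Cost: one sentence of SAP text, these short specifications and a recoding step. No new data are needed.
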